1.1 Primary Aims and Hypotheses

1.1.a. Determine the feasibility and acceptability of a home-based lifestyle activity intervention by assessing recruitment, retention, adherence rates, and participant satisfaction, and monitoring adverse events. We hypothesize that we will meet the accrual target of older cancer survivors within 18 months, retain 80% of the sample, and achieve 80% adherence/fidelity to the intervention with high satisfaction ratings, while limiting the number of adverse events.

1.1.b. Estimate effect sizes for primary and secondary endpoints for the adoption (baseline to 12 weeks) and maintenance (3-months post-intervention) of the intervention. We hypothesize that compared to the control condition, the intervention will result in improvements in physical function (primary outcome) and secondary outcomes: physical performance, objective measures of sedentary- and light-intensity activities, and self-reported quality of life. Further, we hypothesize that the arm differences at 12 weeks will be sustained at 3-months post-intervention.

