Follow-up assessment: The ActivPAL3™ monitor, and instructions will be mailed to all participants to collect 1-week of data for secondary outcomes during week 13. The packet will also include questionnaires to assess subjective outcomes (see **Table 2**). The RA will call to review the instructions and answer any questions. The same procedure will be used for the 3-month post-intervention follow-up assessment.

Participant Advisory Board (PAB): The PAB will include 4-5 cancer survivors from the community. The PAB will meet twice per year (years 2-5) with the study team to provide advice and guidance on the protocol and study materials for both the validation study and RCT, interpretation of the study/RCT results, and identify next steps and strategies for the future, larger RCT (R01 application).

Study Flow: The table below describes the flow of the study from recruitment through intervention delivery to assessment of outcomes. Form of contact (phone, email, or mail) is indicated. Important information is conveyed over the phone (e.g., eligibility assessment, consent) and the use of email is dependent on participant preference for minor communication (e.g, reminders).

Fees/ Postage	Phone		Email		Mail	
	IN	OUT	IN	OUT	IN	OUT
\$					X	NMTR-> mail letter about study & flyer
	(X)		(X)		(X)	(Possible reply by potential ppts)

PROTOCOL TITLE: Whole-of-Day Approach to Physical Activity in Older Cancer Survivors

Fees/ Postage	Phone		Email		Mail		
	IN	OUT	IN	OUT	IN	OUT	
							NMTR releases contact info to Study Team
\$					X		Mail letter of invitation, flyer, & consent form
		X		X		X	Recruitment materials to community settings
	(X)		(X)		(X)		Possible reply by potential ppts
		X					Investigator determines interest & eligibility using REDCap recruitment screener 
 • If refusal → Refusal Qs • If interested & eligible → Go to ppt info
		X					Schedule time to review consent w/ ppt
\$				(X)		(X)	Mail or email consent form (if lost copy)
		X					Review consent
\$			X		X		Ppt mails signed consent form or e-signs
						X	Mail ppt photocopy of signed consent form ¹
		X					Once received, investigator contacts ppt to schedule BASELINE assessment, preference for surveys ² (see Assessment Call 1 Script ...)
							Verify receipt of packet and schedule remote assessment w/ [name] via MYHealth calendar (see Assessment Call 2 Script ...)
\$				(X)		X	Survey packet & cover letter mailed to ppt (optional: email w/ REDCap link)

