PROTOCOL TITLE: Whole-of-Day Approach to Physical Activity in Older Cancer Survivors

classification of accelerometer data. Accelerometer methods will be published according to guidelines.⁸⁰⁻⁸²

Aim 1 - Feasibility & Acceptability: For this feasibility study, we hypothesize that we will meet the accrual target of 64 inactive, older cancer survivors within 18 months, retain 80% of the sample, and to achieve 80% adherence/fidelity to the intervention. No formal statistical analyses are needed for these hypotheses.

Aim 2 - Preliminary estimates of effect sizes: We hypothesize that physical function scores will improve in the intervention group compared to the control group. We will obtain means and precision estimates for between-arm differences in physical function scores at each time point. A linear mixed-effects model will be used with group, time, and group by time interaction, adjusted for ethnicity, rural/urban status, and baseline values as needed. The appropriate variance-covariance structure will be selected to account for the potential correlation among repeated measurements from the same participant. The primary test of interest is the group by time interaction, indicating whether there was a difference between groups in the primary outcome over time. Similar analyses will be conducted for secondary outcomes.

Aim 3 - Process evaluation: will be conducted via a mailed survey. Process data (**Table 2**) and other study related outcomes will be reviewed with the PAB to identify next steps and strategies to ensure the most appropriate design and methods for the future, larger RCT, with potential for broad dissemination and implementation.

PROTOCOL TITLE: Whole-of-Day Approach to Physical Activity in Older Cancer Survivors

Power / Sample Size Calculation

Using a 2-sided, 2-sample t-test, with a significance level of 0.05 and 25 people per arm, we will have 80% power to detect a mean difference of 8.1 in physical function scores (a large effect size) with a standard deviation of 10. To allow for 20% attrition, we plan to enroll and randomize 32 participants per arm. The results of the feasibility trial will inform the design (sample size, effect size) of a larger trial powered to examine efficacy

Maintaining Confidentiality

The following steps will be taken to secure the data and to maintain confidentiality:

- Study participants will be assigned a unique study ID.
- All data collected will be identified with the unique study ID.

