14.0 Potential Benefits to Subjects

The current state of physical activity research is as follows: a) regular physical activity has numerous benefits; however, only a minority of older adults, including older cancer survivors, are physically active at the recommended levels, b) sedentary behavior, especially prolonged periods of uninterrupted sitting, has deleterious effects on health, even among individuals who exercise, and c) light-intensity activity is associated with better physical

PROTOCOL TITLE: Whole-of-Day Approach to Physical Activity in Older Cancer Survivors

health and psychosocial well-being. Since older cancer survivors spend up to 70% of waking hours in sedentary activities and seldom exercise, a potential benefit of participating in the proposed study is behavior change leading to increased light-intensity physical activity and reduced sedentary time. Additional potential benefits include improved physical function and quality of life. The proposed intervention is aimed at determining the feasibility and acceptability of a novel intervention to increase light-intensity activity throughout the day, ideally through at least minimal bouts of stepping each hour. If the intervention is feasible and acceptable to participants, and the data show promise, then this approach could be used to encourage inactive cancer survivors to adopt and maintain an active lifestyle, and may ultimately provide the impetus for further improvements in activity level through increased duration (longer bouts of continuous ambulation/activity) and/or intensity.

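### Does the pilot need a planned confidence-interval width and a rule for passing its effect estimate to the larger trial?

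*Combined protocol and SAP*

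**What the plan says.** Section 1.1 (aim 1.1.b) makes it a primary aim to "Estimate effect sizes for primary and secondary endpoints". Section 10.0, under Power / Sample Size Calculation, sizes the pilot by a test: "Using a 2-sided, 2-sample t-test, with a significance level of 0.05 and 25 people per arm", giving "80% power to detect a mean difference of 8.1 in physical function scores (a large effect size) with a standard deviation of 10". It then raises the number to 32 randomized per arm to cover 20% attrition, and closes with "The results of the feasibility trial will inform the design (sample size, effect size) of a larger trial powered to examine efficacy".

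The Aim 2 analysis in section 10.0 is headed as preliminary estimation and commits to an estimate with its uncertainty: "We will obtain means and precision estimates for between-arm differences in physical function scores at each time point". It also says "The primary test of interest is the group by time interaction". Section 14.0, on benefits to participants, contains the phrase "If the intervention is feasible and acceptable to participants, and the data show promise". The route to a larger trial is described only in general terms: the study timeline (section 7.0) lists preparing a grant application, and section 10.0 (Aim 3) has the advisory board review process data and other study outcomes. Nowhere is an expected interval width given, nor a quantitative rule for using the estimate.

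**The concern.** A pilot whose stated product is an effect size would usually be justified by how well it estimates that effect. This one is justified by power for an effect the plan itself calls large, which speaks to a test. Since effect size is named as something the larger trial will take from the pilot, a reader may suppose that the observed difference will go straight into the next sample-size formula. With 25 completers per arm, sampling error would then largely decide the size of the larger trial. A chance high estimate would give an underpowered trial. A non-significant pilot might lead the team to drop a useful intervention. The prominence given to the interaction test, and the undefined reference to promising data in section 14.0, make that reading easier to reach.

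**Working it through.** **Inputs from section 10.0.** Two-sided two-sample t-test, alpha 0.05, 25 completers per arm, difference 8.1, SD 10, attrition 20%. The SD of 10 matches the PROMIS T-score scale described in Table 2.

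**Assumptions (not in the documents).** Baseline-to-follow-up correlation r of 0.5, 0.7 or 0.8. True standardized effect d of 0.2, 0.3, 0.5 or 0.8.

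**1. The plan's own figure.** d = 8.1/10 = 0.81. Noncentrality = 0.81 × √(25/2) = 2.86 on 48 df, which gives power of 80.1%. Attrition: 25/0.80 = 31.25, rounded up to 32 per arm. Both agree with the plan.

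**2. The precision this implies.** Half-width = t(0.975, 48) × √(2/25) = 2.011 × 0.283 = 0.569 SD.

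| Case | 95% half-width at SD 10 |
|---|---|
| 25 per arm, unadjusted | 5.7 points |
| 32 per arm, unadjusted | 5.0 points |
| 25 per arm, baseline-adjusted, r = 0.5 / 0.7 / 0.8 | 4.9 / 4.1 / 3.4 points |

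The standardized unadjusted width at 25 per arm stays at 0.569 whatever the SD. At SD 5, for example, it is 5 × 0.569 = 2.8 points. The power statement and the width carry the same information: the difference detectable with exactly 80% power is 0.809 SD, and 0.569/0.809 = 0.70. Stating the width would add no new fact about the design.

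**3. What an estimate would look like.** Inverting the noncentral t, an observed d of 0.5 has a 95% interval of -0.07 to 1.06, and an observed d of 0.81 has one of 0.23 to 1.38. The interval is wide, but it is valid and will be visible in the report.

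**4. If the point estimate sized the larger trial.** For 80% power, n per arm is about 2 × (1.96 + 0.84)²/d². At an observed d of 0.81 this is 24 per arm; at the interval limits it is 301 and 9. A trial sized this way has true power below 50% when the observed d exceeds about 2.80/1.96 = 1.43 times the true d. With t-test power for the larger trial and no baseline adjustment, the probability of that is:

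| True d | Chance of under 50% true power |
|---|---|
| 0.2 | 38% |
| 0.3 | 33% |
| 0.5 | 23% |
| 0.8 | 13.5% |

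Baseline adjustment lowers these chances. At d = 0.8 with r = 0.7 the figure is 6.7%.

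**5. If significance decided whether to proceed.** A t-test at one time point among 25 completers per arm has 41% power at d = 0.5 and 18% at d = 0.3. This is not the planned analysis, which is a mixed model over repeated assessments, by intention to treat, with multiple imputation. The figures are only a rough guide.

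**6. Do the documents contain the rule that steps 4 and 5 need?**
- Sizing on the point estimate: section 10.0 says only that results will inform the design. It does not say the observed effect will be used directly.
- Proceeding only if significant: no such criterion appears. The phrase in section 14.0 introduces a statement that the approach could be used to encourage inactive survivors to be active. It describes possible benefit and does not set a threshold for launching a trial.
- Reporting uncertainty: already planned under Aim 2.

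The pilot also supplies an input it estimates reasonably well. With 48 df the 95% interval for the SD runs from 0.83 to 1.25 times the estimate.

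**The case for a change.** The best case for a change is that the feasibility label does not excuse the gap. The plan goes beyond feasibility: it makes effect estimation a primary aim, names effect size as a design input and schedules a grant application. A few sentences fixed before outcome data are analysed would guard against a badly sized successor, and the pilot's sample size would not change. Such text could state the expected width, base the larger trial's target on an important difference, take mainly the SD, baseline correlation and retention from the pilot, and say that the p-value does not decide whether to proceed.

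Part of this stands. The omission is real, the 0.57 SD width is correct, and sizing a trial on a small pilot's point estimate is poor practice. But a width sentence alters no result, and the other elements are choices on which competent statisticians differ. Calling the interaction test exploratory would change the standing of an outcome that section 8.0 lists as a primary endpoint, and the power statement would then need to be reconciled with it. Using the Aim 1 hypotheses as criteria for proceeding would need thresholds that section 1.1 does not give for satisfaction or adverse events. An important difference would have to be chosen, and the documents supply none. These decisions belong mainly to a future trial outside this protocol.

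**Conclusion.** No change is needed. The plan leaves a detail open that the designers of the larger trial can be expected to settle sensibly. The sample-size arithmetic is right, precision will be reported, and the expected half-width of 0.57 SD unadjusted (0.49 to 0.34 SD with baseline correlations of 0.5 to 0.8) follows from numbers already given. The risk of an underpowered successor, 13.5% to 38% over assumed true effects of 0.8 down to 0.2 without adjustment, depends wholly on a sizing rule that the documents do not state. If the protocol is followed as written, the pilot's effect estimates, their intervals and its feasibility conclusions are unaffected. This would be different if the documents said that the observed effect would size the larger trial, or that significance would decide whether it goes ahead. They say neither.

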11.0 Provisions to Monitor the Data to Ensure the Safety of Subjects

This study does not involve the testing of pharmacologic agents nor any therapeutic treatments. It is a behavioral intervention aimed at promoting physical activity using a whole-of-day approach, i.e., increasing light-intensity physical activity throughout the day while reducing and disrupting sedentary activities. Thus, it is classified as a Type 3 Study (Non-therapeutic, non-physical intervention), a minimal risk level study.

PROTOCOL TITLE: Whole-of-Day Approach to Physical Activity in Older Cancer Survivors

For the physical performance tests, the safety of subjects will be monitored in real-time, i.e., during the performance of the brief, timed tests. The study team will not allow the test to start or will stop it early if they believe there is a risk of injury to the participant, e.g., if participant is feeling dizzy, is not feeling well, or has recently suffered an injury that could affect the participant's ability to safely perform the tests.

Study participants will be encouraged to report any “emergencies or events” by calling the toll-free study number. Study staff will record all reported events in the adverse event log (including the subject’s name, date, and event description) and inform the principal investigator, [name], immediately of any unanticipated study deaths or serious events that potentially jeopardize participation in the study. [name] will consult with her mentors/Co-Investigators on the action that should be taken. This communication will occur within 24 hours (for an unanticipated study death), and four business days for an unanticipated serious event. This action and date of implementation also will be recorded in the adverse event log. During the quarterly meetings, the PI and her mentors will classify any reported events as “serious” or “non-serious” (see classification below), as well as “non-attributable”, “possibly attributable” or “attributable” to the intervention (unlike a pharmaceutical trial where known side effects exist, the classification of “expected” vs. “unexpected” is inappropriate for this behavioral intervention).

Serious—any event or condition that is life threatening, results in overnight hospitalization, cancer or a physical or cardiac event serious enough to require medical attention. A brief listing follows:

Fatal

Life threatening

Permanently disabling

Required or prolonged (overnight) hospitalization (Admission—not ER visit)

Overdose

Significant hazard to patient

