8.0 Study Endpoints

Primary endpoints include: a) process data (enrollment, retention and adherence rates; satisfaction with the program), and b) change in self-reported physical function.

Secondary endpoints include change in: a) subjective and objective measures of sedentary- and light-intensity activities, b) physical performance, and c) self-reported quality of life (QOL).

Safety endpoints:

All adverse events associated with the physical performance tests (see section 9.0) will be tracked. The performance tests incorporate movements typically undertaken during normal daily activities (standing from a chair, sitting on a chair), and thus represent tests that are more likely to be safely performed in the home. A friend or family member will be present during the remote assessment of physical performance, which is conducted in the study participants' homes. Safety checks will be made prior to the performance tests (see section 13.0 Potential Risks to Subjects / Protection Against Risks).

Additionally, study participants will be encouraged to report any “emergencies or events” by calling the toll-free study number. See Data Safety and Monitoring Plan for more details.

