Once the study team connects a Fitbit account to Fitabase, Fitabase collects all new data that is collected by the device. When the device syncs (i.e., transfers data), Fitabase is notified of data availability, requests the new data, and then processes the data in order to make it available to the study. The study team will download study participant's de-identified data from Fitabase. Fitabase does not collect personally identifiable data. Each study participant is de-identified with a participant ID. Fitabase does not receive the associated email address, the Fitbit account name, Fitbit Friends list, or any GPS data.

Participants will be given Fitabase's Terms of Use and the Privacy Policy upon request. By consenting to use the Fitbit device as part of this study, the participant also consents to the Fitabase Terms of Use and Privacy Policy. At the end of the study, the participant gets to keep the Fitbit device and will receive instructions how to change the email address associated with the Fitbit account. At the end of the study or if a participant withdraws from the study we will disassociate the Fitbit account from the Fitabase account.

Health Coach Calls / MI: Research assistants will undergo MI training specific to this study. MI techniques and micro-skills will be used to guide five sessions of telephone-based health coaching, which will occur during weeks 3, 5, 7, 9, and 11. Key intervention topics and techniques include: establishing rapport; eliciting knowledge about adverse effects of inactivity/SB and benefits to becoming more active; assessing motivation, confidence, perceived importance and barriers to becoming more active; eliciting change talk; and enhancing participants' self-efficacy (competence) and motivation to be more active (e.g., small, achievable goals). The health coach also provides tech support to the participant for assessments (activPAL and performance testing) and using Fitbit with their mobile app (weeks 1, 2, 13, & 26). The first call (week 2) to help the participant set up their Fitbit may take up to 45 minutes, but can be much shorter depending on the participant's comfort level with technology. The first health coaching call may take up to 45 minutes (week 3); the remaining four health coaching calls will take 20 minutes each (weeks 5, 7, 9 and 11). Health coaching calls will be audio recorded and reviewed for quality control. Audio files will be destroyed 3 years after the study closes.

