Educational Materials: Participants will be mailed educational materials (visual aids) to be used during the telephone calls with their Health Coach. The handouts include: (a) the benefits of LPA and suggestions for how to add more steps to their day, throughout the day (i.e., breaking up sedentary time through at least minimal stepping each hour); (b) reasons to be physically active; (c) example plans for meeting step goals; (d) ideas for getting more steps; and (e) pages for the participant to write their plan for each week. Instructions for setting up and using the Fitbit Inspire 3 tracker and mobile app will be included. All materials serve as reference for discussions with the health coach.

Intervention Fidelity: We will use evidence-based MI training procedures identified in previous studies.^{50,51} The health coaches will receive an initial 1.5 days of in-person MI training by [name] (consultant, clinical psychologist). Prior to contacting participants, the coaches will complete 4 practice sessions, and receive feedback via 4 phone supervision sessions. [name] will code the sessions for MI fidelity by using the MI Treatment Integrity Coding System, version 4.1,⁵² and use this information during supervision sessions. During the study period (15 months), the health coaches will submit one audio recording and participate in one phone supervision per week (months 1-2), then per month (months 3-15). An intervention fidelity checklist will be created to assess the other intervention components, i.e., promoting and supporting self-efficacy, knowledge and skills, self-monitoring, autonomous motivation, and social support to become more active. With HSC Affiliate status, [name] will review the selected audio files saved to the secured P drive.

A Waitlist Control was selected to help boost recruitment and retention. Participants will be asked to maintain their usual lifestyle during the 12-week intervention. After the 12-week waitlist period, participants will receive (via mail) a Fitbit Inspire 3™ monitor and education materials, and the full telephone-based MI intervention with the health coach.

Retention: To enhance recruitment, retention, and adherence rates and to compensate participants for their time and offset phone data charges, a \$50 merchandise card will be provided for each outcome assessment (\$150 total). Additionally, both groups will be able to keep the Fitbit activity tracker after the study ends.

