		X					Reminder to ppt about assessment (text from [name] with link to Zoom or Skype videoconference session for physical function tests)
							Remote assessment conducted / completed via Skype or Zoom

PROTOCOL TITLE: Whole-of-Day Approach to Physical Activity in Older Cancer Survivors

Fees/ Postage	Phone		Email		Mail		
	IN	OUT	IN	OUT	IN	OUT	
		X					Follow-up for incomplete surveys; return of activPAL (see Assessment Call 4 Script ...)
						X	Mail gift card (after verifying activPAL returned, and remote assessment AND surveys completed)
						X	Mail letter to immediate intervention group (maintain usual activity; next study contact in 12 weeks)
							Start intervention for waitlist control participants (Fitbit setup, 5 health coaching calls)
							26-week assessment 
 • Schedule remote assessment w/ [name] via MYHealth calendar • Ask survey preference (mail/online)
							Repeat steps from 13-week assessment
							Post-study telephone survey

NOTES:

¹ Whoever conducts the consent process signs the participants' form once received; for e-consent; print consent form, sign, photocopy and keep one copy in the ppt's folder; mail a copy of signed consent to ppt

² Whoever conducts the consent process signs the participants' form once received; for e-consent; print consent form, sign, photocopy and keep one copy in the ppt's folder, mail a copy to ppt

PROTOCOL TITLE: Whole-of-Day Approach to Physical Activity in Older Cancer Survivors

Outcomes and Measurements

All measures have well-established validity and reliability, and are responsive to change.

Table 2. Outcomes & Measures (B=baseline; P=1-week post-intervention; F=3-months post-intervention follow-up to assess maintenance of behavior change & effects)(alpha=Cronbach's alpha; ICC=intraclass correlation test-retest reliability; RMSEA=root mean square error of approximation; CFI: comparative fit index)	B	P	F
Process Data (primary outcomes): As this is a feasibility and acceptability study, the primary outcomes relate to recruitment, retention, adherence, and adverse events, which will be carefully tracked. Collected and used to evaluate adherence: steps per day/number of active hours (downloaded from Fitbit® website), satisfaction with the program, likes & dislikes, barriers & issues, perceived degree of benefit, and intervention fidelity (see above)		X	X

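### Adverse events are a primary feasibility outcome, but outside the supervised tests they are captured only if reported, and between assessments staff calls go only to the arm being coached

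*Combined protocol and SAP*

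**What the plan says.** Safety belongs to the primary question. Aim 1.1.a (Section 1.1) hypothesizes that the feasibility targets will be met "while limiting the number of adverse events", with no numeric limit. Section 3.0 counts safety of the intervention among the primary aims. The process data row of Table 2 (Section 9.0) states that "the primary outcomes relate to recruitment, retention, adherence, and adverse events, which will be carefully tracked", and marks that row for the post-intervention and follow-up time points.

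The collection method is narrower. Section 8.0, under safety endpoints, says: "All adverse events associated with the physical performance tests (see section 9.0) will be tracked". Sections 8.0 and 11.0 invite participants to report anything else "by calling the toll-free study number", and in Section 11.0 "Study staff will record all reported events in the adverse event log". Section 8.0 also points to a Data Safety and Monitoring Plan for more detail.

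Contact between assessments depends on the arm. After a week-2 call to set up the tracker, the immediate arm has "five sessions of telephone-based health coaching, which will occur during weeks 3, 5, 7, 9, and 11". For the waitlist arm, "Participants will be asked to maintain their usual lifestyle during the 12-week intervention". After week 13 the Study Flow table gives the waitlist arm the set-up and five coaching calls. Table 3 leaves the immediate arm without study contact in weeks 14–25 while it maintains its goals.

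**The concern.** The intervention is unsupervised: up to 3,000 extra steps a day in people aged 65 or over who are selected for impaired physical function. The events of most interest, such as falls, injuries and new pain, would mostly happen away from the brief supervised tests. The visible plan has no scheduled question, checklist or recall period for them. Minor events in particular may never prompt a telephone call.

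Two things follow. A small number of logged events could mean a well-tolerated programme or could mean non-reporting, and the plan has no way to tell these apart. Also, someone who speaks to a coach every two weeks has more openings to mention an event than someone who does not, so the chance of being recorded may differ by arm and period. Section 10.0 uses the trial's results to inform the design of a larger trial, so a misleading safety count would be carried forward.

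**Working it through.** **The plan's own figure.** The only computed figure is the sample size in Section 10.0. A two-sided two-sample t-test at 0.05 with 25 per arm, difference 8.1 and SD 10 has 80.1% power, and 25 / 0.80 = 31.25, rounded up to 32 per arm. It reproduces. It does not bear on adverse events, for which the plan gives no figure. I use 32 only as the arm size.

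**Scheduled contacts, counted from Section 9.0 (Health Coach Calls, Waitlist Control, Follow-up assessment, Table 3, Study Flow).**

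| Period | Immediate arm | Waitlist arm |
|---|---|---|
| Weeks 2–12, set-up and coaching calls | 1 + 5 = 6 | 0 |
| Week 13 assessment | calls and videoconference | same |
| Weeks 14–25, set-up and coaching calls | 0 | 1 + 5 = 6 |
| Week 26 assessment | calls and videoconference | same |

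Over 32 participants, the first period has 6 × 32 = 192 calls against 0, and the third has the reverse. Contact at the assessments is equal.

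**Possible distortion between arms.** The documents give no capture rates, so these are assumptions: a share *s* of events is logged without coaching calls (30–50%) and a share *c* with them (50–90%). If the true risk *p* is the same in both arms, expected logged events are 32 × *p* × *s* and 32 × *p* × *c*, and the artificial ratio is *c* / *s*, whatever *p* is. With an assumed *p* of 20% (6.4 true events per 32):

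| *s* | *c* | Logged, uncoached | Logged, coached | Gap | Ratio |
|---|---|---|---|---|---|
| 0.30 | 0.50 | 1.9 | 3.2 | 1.3 | 1.67 |
| 0.30 | 0.90 | 1.9 | 5.8 | 3.8 | 3.00 |
| 0.50 | 0.70 | 3.2 | 4.5 | 1.3 | 1.40 |
| 0.50 | 0.90 | 3.2 | 5.8 | 2.6 | 1.80 |

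Across these four pairs the spurious gap is about 0.6–1.9 events per 32 at *p* = 10% and 2.6–7.7 at *p* = 40%. If the calls elicit nothing extra, *c* = *s* and the ratio is 1.0.

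**Under-counting, with no arm comparison.** The chance of logging no event among 32 people is (1 − *p* × capture)^32. With an assumed *p* of 10%:

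- capture 100%: 0.90^32 = 0.034, or 3%
- capture 50%: 0.95^32 = 0.194, or 19%
- capture 30%: 0.97^32 = 0.377, or 38%

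**The case against.** The strongest reply is that the plan collects more, and more symmetrically, than Section 11.0 suggests. Both arms have the same calls and videoconference at weeks 13 and 26. A fall assessment precedes the performance tests (Section 13.0), and staff must judge whether a recent injury makes them unsafe (Section 11.0). PROMIS pain and a 42-item list of conditions and symptoms are collected in both arms at each assessment, and a post-study telephone survey is listed. Events during the tests are observed in real time. All of this stands, and it rules out saying that staff contact exists only in the coached arm. But nothing shows that these sources feed the adverse event log. The fall assessment is there to decide how many helpers stand nearby, and the Falls Efficacy Scale measures concern about falling, not falls.

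A reader might also infer that capture tracks exposure exactly. It does not: after week 13 the coaching calls switch arms, but the immediate arm is still asked to maintain its goals. Nor do the documents say that coaches ask about events, so higher capture during coaching is an assumption.

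No between-arm adverse event comparison is planned, and the Aim 1 analysis in Section 10.0 has no formal test. The arm ratio therefore matters only if someone draws that comparison. The under-counting calculation does not depend on it.

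Finally, the assessment call scripts and any separate Data Safety and Monitoring Plan are not among the documents. Either may already hold a query.

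**Conclusion.** The concern holds as a risk, not as a demonstrated bias. For a primary feasibility outcome, the visible plan relies on unsolicited reports outside the supervised tests, and opportunities to report between assessments are concentrated in the arm being coached. Under the assumed capture rates the artificial arm ratio is about 1.4 to 3.0, falling to 1.0 if coaching calls add nothing. At an assumed 10% true risk, the chance of an empty log in an arm of 32 rises from 3% to 19–38%.

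It would go too far to say that the counts are too low, that they differ by arm artificially, or that the trial cannot answer its safety question. Each needs capture rates that the documents do not give. What can be said is that a limited count would be hard to interpret. The change is worth making because it is cheap. The sample size is unaffected.

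Separately, Section 8.0 and Table 2 disagree on whether adverse events are safety or primary endpoints and on how widely they are tracked.

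**What to change.** 1. Check the Data Safety and Monitoring Plan and the assessment call scripts. If a uniform query exists, describe it in Section 11.0 and go to step 3.
2. Otherwise add one scripted question to the week-13 and week-26 contacts in both arms, covering falls, injuries, new pain and hospital admissions since the last assessment. Enter the answers, and the result of the existing pre-test fall assessment, in the adverse event log.
3. Count events from every source, including those in participants who withdraw or die before the call. Elicited answers alone would miss these people; at the planned 20% attrition that could be 0.20 × 32 = 6.4, about 6 per arm.
4. Record each event's source (elicited, spontaneous or coaching call) and report by arm and period. Use the elicited events for any arm comparison: with equal recall in both arms, the expected artificial ratio is then 1.0.
5. Reconcile Section 8.0 with Table 2 on the status and scope of adverse event tracking.

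The cost is one question in existing scripts and some log entries, with no new visits or staff. The small downside is that more minor events will be logged. This is a cheap improvement.
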